### **Study site Questionnaire**

As this is a real-world study, the procedures and assessments below are not mandated and do not need to occur at a specific interval. All data deemed pertinent to the management of the patients.

## 10 TREATMENTS

The purpose of the study is to capture how Cemiplimab is prescribed and managed for patients with advCSCC in a real-world setting, thus compliance to a specific treatment protocol is not applicable.

The prescription of therapies is under the sole responsibility of the treating physician. No investigational agents will be provided to enrolled patients by the sponsor as part of this study.

The patients who will be enrolled in the study will be selected among the patients for whom the physician has decided to prescribe Cemiplimab independently from study entry.

The treating physician should refer to the SmPC for any information on treatment prescribed.

In addition to (or substituting for) Cemiplimab, patients may receive other therapies as deemed necessary by their physicians for the treatment of advCSCC or comorbid conditions. Any concomitant treatment information will be collected throughout the study.

There are no protocol requirements regarding treatment discontinuation. If treatment with Cemiplimab is discontinued permanently or temporarily, patients will remain eligible and will be encouraged to stay in the study.

## 11 DATA COLLECTION

### 11.1 DATA COLLECTION

The physicians and/or their assigned staff will be responsible for patient identification, qualification and selection, data abstraction and completion of the patient eCRF. Clinical data will be sourced from patient medical records. Patient data will be de-identified and will be reported in aggregate. eCRFs will be programmed to be available online via encrypted, password protected access. The data entry will be checked for consistency and accuracy.

Following a patient's ICF and enrollment in the study, the frequency with which the patient visits his/her primary CSCC provider will be determined by the local SoC.

### 11.2 DATA COLLECTED FOR BOTH COHORTS OF THE STUDY

#### 11.2.1 Patient data

##### **Patient and tumor characteristics and treatment patterns**

Study data will be collected as described in the table "**PARAMETER AND DEFINITIONS for the CRF's**" (see above).

##### **Response**

Best response will be captured as assessed by the study site and may include clinical assessment, radiographic imaging, or symptom resolution. DOR will be defined as time from the time of initial response until documented tumor progression or death.

Study data will be summarized descriptively with consideration for the following:

- Time to next of treatment (TTNT) or death, ORR, Disease Control Rate (DCR), DOR, Time to respond, PFS, OS,
- TTTF including lack of response and discontinuation due to AE
- Incidence and timing of pseudo progression, if applicable
- Response after pseudo progression, if applicable
- Time to response following occurrence of pseudo progression, if applicable
- IrAEs, SAEs

- DSD
- Pain Reduction

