### Primary objectives

*Prospective and retrospective cohort:* Primary objective for this Cemiplimab NIS is to evaluate the clinical outcomes in treatment of advCSCC as a result of TTNT. Assessments of the response are clinical observations of physician's choice.

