### Secondary objectives of the prospective cohort

- DOR to identify and describe long-term effects of treatment of patients with CSCC
- DCR (CR+PR+SD) at 3, 6, 9, 12, 18, 24, 36 months
- To assess patient experience, functional status, QoL and pain, in a real-world setting for patients with advCSCC at 3, 6, 9, 12, 18, 24 and 36 months
- To collect and describe safety data on study participants
- To describe patients who receive Cemiplimab as treatment for advCSCC in a real-world setting
- OS defined as duration from current mCSCC or ladvCSCC diagnosis and also from the initiation of each LOT until death or end of follow up
- Proportion of patients surviving at month 3, 6, 9, 12, 18, 24 and up to months 36 from initiation of systemic therapy
- PFS defined as time from first documented systemic cemiplimab therapy initiation until progression or treatment discontinuation due death or end of follow up
- Patient demographics and baseline characteristics (incl. age, performance status etc.) at study entry
- Characterization of Cemiplimab usage patterns
- Cemiplimab treatment regimen (initial dose and date of initiation and regimen changes)
- Treatment prior to and post Cemiplimab treatment, incl. surgery, radiation, systemic therapies incl. agents administered, dose, frequency and duration

- Surgery post initiation of Cemiplimab treatment
- DOT
- TNM stage (AJCC or UICC)
- Analysis of Cemiplimab tolerability and safety profile in daily clinical practice
- Observed rates, reasons and timing of the discontinuation of Cemiplimab
- TTF including lack of response and discontinuation due to AE
- Analysis of change in patient reported QoL as per EORTC-QLQ-C30 QoL questionnaire during treatment with Cemiplimab (for prospective cohort only)

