### 7.3 EVALUATION CRITERIA

Study examinations will take place at months 3, 6, 9, 12, 18, 24 and 36.

Survey of concomitant medication and Cemiplimab treatment will take place at all study examinations.

Tumor Evaluation will be conducted according to guidelines and evaluation according to RECIST v.1.1 (Appendix 16.2). Computed tomography (CT) scan or magnetic resonance imaging (MRI) of chest, abdomen and pelvis and additional tumor bearing areas as well as digital photography of cutaneous lesions are preferred methods.

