	Immunosuppressive therapy		
	Substantial tumor syndromes		
	Specification of substantial tumor syndromes		
	Disease & medication		
Primary diagnosis	Date of diagnosis		All primary diagnosis at Baseline
	Evaluation		
	Tumor status		
	Histological subtype		
	Tumor localization		
	TNM classification		
	Clinical stage		
	ECOG performance status	Defined as 0, 1, 2, 3, 4, measured at advanced diagnosis, at each LOT, prior to and following radiation for early disease, where applicable	
	Infiltration depth and bone involvement		
	Initial treatment of primary tumor		
	Primary surgery	If yes: date, procedure	
	Re-excision	If yes: date, procedure, micrographic controlled surgery, final resection border, cumulative safety distance (cm)	
	Tumor size of the histo block	horizontal tumor diameter (cm), vertical tumor size (mm), differentiation level	
	High risk factors		
	Further synchronous CSCC		
	Curative surgery of advCSCC	Yes or no	
	Tumor board	Yes or no. If yes: decision realized (yes or no)	
	Metastases	Locoal regional or distant	
Recurrence	Date of diagnosis		All recurrence

diagnosis			diagnosis at Baseline
	Evaluation		
	Tumor status		
	Histological subtype		
	Tumor localization		
	TNM classification		
	Clinical stage		
	ECOG performance status	Defined as 0, 1, 2, 3, 4, measured at advanced diagnosis, at each LOT, prior to and following radiation for early disease, where applicable	
	Infiltration depth and bone involvement by local recurrence		
	Initial treatment of primary tumor		
	Primary surgery	If yes: date, procedure	
	Re-excision	If yes: date, procedure, micrographic controlled surgery, final resection border, cumulative safety distance (cm)	
	Tumor size of the histo block	horizontal tumor diameter (cm), vertical tumor size (mm), differentiation level only by local recurrence	
	High risk factors by local recurrence		
	Further synchronous CSCC by local recurrence		
	Curative surgery of ladvCSCC	Yes or no	
	Tumor board	Yes or no. If yes: decision realized (yes or no)	
	Metastases	Locoal regional or distant	
Restaging	Date of diagnosis		All restaging parameters at Baseline
	Evaluation		
	Tumor status		
	Histological subtype		
	Tumor localization		

	TNM classification		
	Clinical stage		
	ECOG performance status	Defined as 0, 1, 2, 3, 4, measured at advanced diagnosis, at each LOT, prior to and following radiation for early disease, where applicable	
	Infiltration depth and bone involvement		
	Differentiation level		

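### Response follows RECIST 1.1 in one section and physician's or site judgement in two others, and the case report form as shown schedules no dated response category after baseline

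*Protocol*

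**What the plan says.** Three places in the protocol say how response is judged.

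- Section 7.3 (Evaluation criteria): "Tumor Evaluation will be conducted according to guidelines and evaluation according to RECIST v.1.1". CT or MRI and "digital photography of cutaneous lesions are preferred methods".
- Section 6 (Primary objectives, both cohorts): "Assessments of the response are clinical observations of physician's choice".
- Section 11.2.1 (Response): best response is the site's own assessment and "may include clinical assessment, radiographic imaging, or symptom resolution".

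The endpoints that use response are secondary. Sections 6 and 14.3.1.2 list "DCR (CR+PR+SD) at 3, 6, 9, 12, 18, 24, 36 months" and duration of response for the prospective cohort. Section 11.2.1 counts duration of response from the initial response to documented progression or death, and adds time to response and outcomes after pseudoprogression. Section 14.3.2.2 reports ORR with a 95% interval for each cohort and pooled, plus a model for predictors of response.

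For data collection, section 11.2.1 points to the parameter table in section 9. There, a yes/no Response item sits in the Restaging block, whose timing is "All restaging parameters at Baseline". A Best response item sits in the Systemic therapy block, which is also timed at baseline.

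**The concern.** RECIST 1.1, clinical observation at the physician's discretion, and a site judgement that may draw on symptoms are different measures of response. A site reading all three sections cannot tell which one to apply. If the basis is not recorded, the analyst cannot separate them later.

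The second difficulty is the schedule. A baseline entry cannot hold the response to a treatment that is only then being started. A yes/no entry cannot separate stable from progressive disease, which the disease control rate requires. An analysis plan can choose a definition, but it cannot supply a category, date or method that was never collected.

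What is at stake is how far the prospective response endpoints can be interpreted, and whether the two cohorts' ORRs can sensibly be shown side by side and pooled.

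**Working it through.** The protocol gives no figure for this point, so the check is mainly a comparison of texts.

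**Step 1: the stated basis for response.**

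| Place | Basis | Force |
|---|---|---|
| Section 7.3 | RECIST 1.1 | Stated as what will be done; imaging and photography only preferred |
| Section 6, primary objectives | Clinical observation, physician's choice | Stated as a fact, both cohorts |
| Section 11.2.1 | Site assessment; clinical, radiographic or symptomatic evidence | Permissive, both cohorts |

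Section 7.3 refers for RECIST to an Appendix 16.2. In this document 16.2 is the section on laws and regulations, and the only appendix is the amendment history, so the reference settles nothing. The Restaging block has an entry labelled Evaluation, but it has no definition and is also timed at baseline. No item is therefore defined to record the basis of a response.

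**Step 2: what each endpoint needs, and what is scheduled after baseline in the text shown.**

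| Endpoint | Needs | Scheduled in section 9 |
|---|---|---|
| Disease control at months 3, 6, 9, 12, 18, 24, 36 | Response category at each of 7 visits | Progression and its date only |
| Duration of response | Date of first response; date of progression or death | The end date only |
| Time to response | Treatment start; date of first response | Treatment start only |
| ORR, prospective | Best response to cemiplimab | Best response item, timed at baseline |
| ORR, retrospective | Best response on the therapy given | Available at the single documentation; method not recorded |

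Progression is scheduled at months 3 to 36, but is defined by the medical record, with no mention of RECIST. The visit timetable at the end of section 9 marks tumour-related history and current TNM at every visit and has no row for response.

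Progression alone does not give disease control. A patient without recorded progression may have CR, PR or SD, or may not have been assessed, and these cannot be told apart.

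**Step 3: scale, as illustration only.** Take an ORR of 45%, between the 43.6% and 47% cited in section 5.1, and assume all 200 patients of a cohort are evaluable.

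- Half-width of the 95% interval: 1.96 × √(0.45 × 0.55 / 200) = 0.069, or 6.9 points. At 43.6% and 47% it is also 6.9 points.
- Effect of classing 10 patients differently: 10 / 200 = 5 points.

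The 10 patients are an assumption. The protocol gives no rate of responses judged on symptoms or clinical impression alone. Each further 1% of patients classed differently moves ORR by 1 point.

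**The case against.** The case on the other side has several sound parts.

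- Site-assessed response is normal in a non-interventional study. Section 9 says assessments are not mandated or tied to intervals, and section 7.3 only prefers imaging. The section 6 sentence also stands under the TTNT objective. This makes a looser basis legitimate, but does not reconcile it with the firm RECIST statement in section 7.3.
- The baseline labels are not a reliable list of all that is collected. Read literally, they would confine the Systemic therapy block to baseline, although section 7.3 surveys cemiplimab treatment at every examination and section 7.1 continues documentation of later therapies. The synopsis lists ORR, disease control and duration of response among collected data. Response could be meant to go under tumour-related history, but nothing says so.
- The study flow chart in section 2.2 is not visible and may contain a tumour-assessment row. Absence can be claimed only for the text and tables shown.

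A reader might infer that symptomatic improvement without tumour shrinkage would be counted as objective response and inflate ORR. The text does not support that. Section 11.2.1 permits symptoms as part of the evidence; it does not say that they suffice. A reader might also infer that disease control and duration of response cannot be computed at all. That goes too far, since progression dates are scheduled and a response date may be captured elsewhere.

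**Conclusion.** The point holds in limited form. The three statements on the basis of response conflict, and no item is defined to show which one a given response used. This affects ORR in both cohorts and the pooled rate. In the text shown, the prospective cohort has no scheduled item after baseline for a dated first response or for response category by visit, so disease control at 7 visits, duration of response and time to response lack a stated source. The schedule gap hardly touches the retrospective cohort, where best response can be taken at the single documentation.

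Only secondary, descriptive endpoints are involved. The primary endpoint, TTNT, does not depend on response. The direction and size of any effect on ORR are unknown; the 5 points against 6.9 show scale only.

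A reader might conclude that ORR must rest on RECIST alone in both cohorts. The documents do not support that either: the retrospective data are anonymous charts of patients diagnosed from 2012 to 2019 and documented once, and such a rule could replace misclassification with selective missingness. The conclusion assumes that the eCRF follows the section 9 table and that the unseen flow chart adds no response item.

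**What to change.** 1. Reconcile sections 6, 7.3 and 11.2.1 into one stated response basis per cohort. One option is RECIST 1.1 where imaging or lesion measurement exists, and physician assessment otherwise. Correct the appendix reference in section 7.3.
2. In section 9 and its visit timetable, add response category (CR, PR, SD, PD, not assessed), date and method of assessment at each follow-up documentation from month 3 to month 36. If the flow chart or the eCRF already has such an item, bring the table into line with it.
3. In the retrospective cohort, record best response with its method for each therapy line.
4. Report ORR by method of assessment in each cohort and in the pooled rate, so that responses resting only on clinical judgement or symptoms can be separated from those based on imaging or measurement.

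The cost is a small eCRF change, revised wording and some entries of not assessed. No extra scans or visits are needed, because the change only records what routine care already produces.

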## **12 MANAGEMENT OF DATA**

### **12.1 DATA COLLECTION, VALIDATION AND DATA QUALITY CONTROL AT SANOFI / REGENERON LEVEL**

Data will be collected using e-CRF. QoL questionnaires in electronic format (tablet) will be handed out to the patients. Data of the collected QoL questionnaires will be transferred into the data base electronically by Sanofi or a CRO appointed by Sanofi.

The computerized handling of the data by the service provider may generate additional requests to which the participating physician is obliged to respond by confirming or modifying the data questioned.

### **12.2 MONITORING AND DATA QUALITY CONTROL AT SITE LEVEL**

A monitoring will be realized in according to the appropriate SOP. With regard to the quality assurance 5% of the sites will be controlled in view to the quality of data. Every data of a patient will be controlled in the site. Item of the controlling are the informed consent, some specific parameter and the completeness of the SAE reporting.

## **13 MANAGEMENT AND REPORTING OF ADVERSE EVENTS/ADVERSE REACTIONS**

Procedures for the collection, management and reporting of individual cases of AE/adverse reactions and of any new information that might influence the evaluation of the benefit-risk balance of the product while the observational study is being conducted. Any arrangements made between *Alcedis GmbH* and regulatory authority for the management and reporting of AE/reactions in product observational study should be specified.

If applicable, the exemption process may be followed to define exemptions for the collection of pre-defined AEs which must be described in the protocol and receive Regulatory Authority approval.

All AE regardless of seriousness or relationship to Cemiplimab, spanning from the signature of the ICF form until the end of the study as defined by the protocol (e.g., Long term follow up required by protocol after end of product exposure) for each patient are to be collected by the treating physician and reported to *Alcedis GmbH*. SAE have to be reported within expedited time frame (24 hours of awareness, no later than the following working day), non-serious AE no later than within 30 days of awareness.

Additionally, all AE under any other product of the Sanofi Group must also be reported to PV Sanofi, SAE within 24 hours of awareness, no later than the following working day, non-serious AE no later than within 30 days of awareness.

Furthermore, all AEs generated by the patients QoL questionnaires must be reported to PV Sanofi. These AEs must be entered also in the Sanofi PV database. If patients mention any AE in this QoL questionnaire, the treating physician must document it as a single case and forward it to PV Sanofi.

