## 1 SYNOPSIS

COMPOUND: Cemiplimab (SAR439684)	
STUDY No: OBS16381	
TITLE	Two cohort registry study for patients with advanced CSCC treated with Cemiplimab or other approaches
LOCATION	Approx. 60 sites in Germany, plus 5 sites in Switzerland and 5 sites in Austria
SCIENTIFIC COMMITTEE CHAIR PERSON	[REDACTED]
STUDY OBJECTIVE(S)	
The objectives of the study are
 
Prospective cohort:
 

• To identify TTNT

• To identify potential determinants of disease progression as final outcome, Quality of life (QoL), pain and other health related outcomes for CSCC patients undergoing treatment with Cemiplimab

• To collect long-term effectiveness and describe effects of treatment

• To collect safety data in a real world setting

 
Retrospective cohort:
 

• To examine real-world data of advanced CSCC (advCSCC) patients who were treated before approval of Cemiplimab (treatment approaches, safety, patient characteristics, long-term effects)

 
Primary objective prospective and retrospective cohort:
 
Primary objective for this non-interventional study (NIS) is time to next treatment (TTNT) excluding best supportive care (BSC).
 
Secondary objectives prospective cohort:
 
Patient demographics and baseline characteristics (TNM stage), Cemiplimab treatment regimen, duration of treatment (DOT), prior and post Cemiplimab treatments, response to Cemiplimab treatment (ORR, CR, PR, SD), duration of response (DOR), disease control rate (DCR = CR+PR+SD), time to treatment failure (TTFT), overall survival (OS), progression free survival (PFS), safety data, quality of Life (QoL) incl. pain.
 
Secondary objectives retrospective cohort:
 
Patient demographics and baseline characteristics (TNM stage), effectiveness (ORR, PFS, OS) and safety of different treatment options used routinely for advanced CSCC prior to Cemiplimab launch, patterns

	of treatment.

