**Retrospective Cohort:**

In the retrospective cohort this study will document (1 documentation time point) patients not intended for Cemiplimab therapy and first diagnosed with advCSCC between Jan/2012 and Aug/2019. It will obtain data of anti tumor therapies (prior to Cemiplimab approval) and

[figure not shown]
	
their outcome. We plan to document the disease history including prior surgery, radiotherapy, systemic therapies and the related safety data as well as effectiveness. The largest study with advCSCC was recently published (Hillen et al. 2018), which examined retrospectively 190 patients from Germany and Austria first diagnosed between Jan/2010 and Dec/2011 with a first-time follow-up on May/2014.
 
Within this retrospective cohort, we will collect only anonymous data from patients without Sanofi-ICF. This procedure allows including data from patients who are no longer alive (planned)
 
Patient characteristics (age, sex, diseases, immunosuppression, comorbidities, localization, etc.) and therapeutic modalities will be evaluated (as in the prospective cohort if applicable).
																				

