### **Secondary objectives of the retrospective cohort**

- Description of retrospective patient population, patterns of care and effectiveness of different treatment options used under routine conditions for advanced CSCC prior to Cemiplimab launch
- To collect and describe safety data on study participants
- Proportion of patients surviving at month 3, 6, 9, 12, 18, 24 and up to months 36 from initiation of systemic therapy
- PFS defined as time from first documented systemic therapy initiation until progression or treatment discontinuation due death or end of follow up
- Patient demographics and baseline characteristics (incl. age, performance status etc.) at study entry
- TNM stage (AJCC or UICC)
- Patterns of treatment for the retrospective cohort.

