#### **Premature withdrawal from the study**

A patient has the right to withdraw from the study at any time, for any reason, and without any penalties resulting from this decision.

The participating physician should make every effort to re-contact the patient to determine his/her health status, including at least his/her vital status. In case of Cemiplimab treatment discontinuation at any time, the documentation will continue until month 36 or patient's death to assess outcome and further therapeutic modalities.

For the retrospective cohort: no Sanofi-ICF will be collected.

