	High risk factors		
	Further synchronous CSCC		
	Response	Yes or no	
	Tumor board	Yes or no. If yes: decision realized (yes or no)	
	Metastases	Locoal regional (type, single or multiple) or distant (localization, single or multiple)	
Surgery	Date of surgery		All at Baseline
	Evaluation		
	Marked lymph nodes (sentinel)	Yes or no	
	Surgery procedure		
	Diameter of largest lymph node	(cm)	
	Capsule break	Yes or no	
	Number of removed lymph nodes		
	Number of lymph nodes with metastases	Maximal size (cm)	
	Completing lymph node dissection	Yes or no If yes: date, procedure, number of dissected lymph nodes, number of lymph nodes with metastases,	
	Residual status		
	Global status of the patient	Tumor free (yes or no)	
Systemic therapy	Intention		All at Baseline
	Line	(1st-line, 2nd-line, ...)	

	Regimen		
	Type	(table with medicinal products, table with study medicinal products, table with toxicity)	
	Therapy	From (date) to (date) or ongoing, number of cycles, application,	
	Best response		
	Reason for therapy completion		
	Table with medicinal products	From (date) to (date) or ongoing. Active ingredient / brand name	
	Table with study medicinal products	From (date) to (date) or ongoing. Type, study, study trial	
	Table with toxicity	Date, event term, severity, medical procedure, outcome.	
Locoregional therapy	Date	From (date) to (date)	All locoregional therapy at Baseline
	Medical examination		
	Intention		
	Therapy procedure		
	Residual status	Locoregional efficacy	
	Global status of the patient	Tumor free or do metastases exist at other location?	
Radio Therapy	Date	From (date) to (date)	All radio therapy at Baseline
	Medical examination		
	Intention		
	Organ system		
	Laterality		
	Type		
	Dosage	(Gray)	
	Residual status	Response rate (no, partial, complete)	
	Global status of the patient	do metastases exist at other location?	
Final patient treatment	Date of last visit		Last and final visit at end of follow-up after 36 months

	Reason of last visit		
	Tumor death relation		
	Date of death		

The following table demonstrate a time table for the e-CRF parameter

	Baseline	Start of Treatment	Visits: Month after start of treatment						
			3	6	9	12	18	24	36
Informed consent	x								
Patient characteristics: Gender, age, skin type etc.	x								
Medical History									
- General medical history (comorbidities, etc.)	x		x	x	x	x	x	x	x

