#### **14.3.1.3 Secondary variables of the retrospective cohort**

- \* Characteristics of retrospective patient population, patterns of care and effectiveness of different treatment options used under routine conditions for advanced CSCC prior to Cemiplimab launch
- \* Safety data on study participants
- \* Proportion of patients surviving at month 3, 6, 9, 12, 18, 24 and up to months 36 from initiation of systemic therapy
- \* PFS defined as time from first documented systemic therapy initiation until progression or treatment discontinuation due death or end of follow up
- \* Patient demographics and baseline characteristics (incl. age, performance status etc.) at study entry
- \* TNM stage (AJCC or UICC)
- \* Patterns of treatment for the retrospective cohort.

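### Retrospective safety is an objective, but that cohort has no defined AE collection window, and only systemic therapy has a dated toxicity table

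*Protocol*

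**What the plan says.** **Objective.** The synopsis lists among the secondary objectives of the retrospective cohort the "safety of different treatment options used routinely for advanced CSCC prior to Cemiplimab launch". Its description of the data to be documented for that cohort covers "prior surgery, radiotherapy, systemic therapies and the related safety data as well as effectiveness". Section 6 repeats the aim ("To collect and describe safety data on study participants"), and section 14.3.1.3 makes it a variable: "Safety data on study participants".

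**Collection rule.** Section 13 requires all AEs to be collected "spanning from the signature of the ICF form until the end of the study as defined by the protocol", and section 13.1.3 uses the same start. Under premature withdrawal in section 8.3 the protocol says: "For the retrospective cohort: no Sanofi-ICF will be collected". Sections 1 and 8.2 add that the data are anonymous and may come from patients who have died. The synopsis gives this cohort a single documentation point.

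**CRF.** In section 9 the systemic therapy block has a toxicity table with the items "Date, event term, severity, medical procedure, outcome". The surgery, locoregional therapy and radiotherapy blocks have no toxicity item. A separate generic AE row records whether an event occurred, what it was, whether it was related to anticancer treatment and whether it was serious, as found in the medical record. Section 11.2 applies the CRF table to both cohorts.

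**The concern.** The protocol undertakes to describe safety by treatment option before cemiplimab, but its AE-specific rule is anchored to an event that does not occur in this cohort. Sites abstracting charts are not told from when to when they should look for adverse events. They have a structured place for toxicity of only one of the treatment types that the synopsis names.

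What is at stake is a stated secondary objective for half of the study, not the primary endpoint. If sites follow the CRF as written, systemic therapy will come with dated, graded toxicities, and the other treatments with unlinked entries in a general row. A safety table by treatment option would then partly reflect how events were recorded. Later analysis cannot repair this, because it cannot recover dates and links that sites were never asked to abstract.

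**Working it through.** No stated figure is involved, so the check sets the provisions side by side.

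**1. What the objective needs.** Safety by treatment option needs, for each event, a period in which it was sought, a date and a link to a treatment.

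**2. Which window applies to the retrospective cohort.**

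| Provision | Start | End | Does it cover retrospective AEs? |
|---|---|---|---|
| Sections 13 and 13.1.3 | consent signature | end of study | Names AEs, but this cohort has no consent date |
| Section 7.1, consent subsection | advanced diagnosis | last visit, death or loss to follow-up | Written for the primary objectives; AEs not named |
| Section 9, data collection forms | before advanced diagnosis | last follow-up or death | Names characteristics, treatment patterns, outcomes and resource use; AEs not named |

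The two general periods do not depend on consent, but they start at different points and neither mentions AEs. Section 14 does not settle the matter: 14.3.1.2 refers prospective safety data to section 13, while 14.3.1.3 gives the retrospective variable no definition or reference.

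**3. Where an event can be recorded.**

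| CRF location (section 9) | Event date | Severity | Link to a treatment |
|---|---|---|---|
| Systemic therapy, toxicity table | yes | yes | yes, by its place in the block |
| Surgery | no toxicity item | no | no |
| Locoregional therapy | no toxicity item | no | no |
| Radiotherapy | no toxicity item (response and disease status only) | no | no |
| Generic AE row | not listed | CTCAE 5.0 reference | only whether related to anticancer treatment |

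Section 7.3 asks the investigator to name the suspected treatment, which may be a procedure, but only for immune-related AEs and SAEs. Other surgical or radiotherapy toxicity need not be tied to its treatment. The AE definition in 13.1.1 refers to patients given a pharmaceutical product, so it does not clearly reach a patient treated by surgery or radiotherapy alone.

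**4. When the generic row is filled.** The CRF table schedules it at baseline and months 3 to 36. The e-CRF timetable later in section 9 marks AEs at months 3 to 36 and leaves baseline blank. A cohort documented once has no month 3 to 36 visits. It therefore has one AE slot under the CRF table and none if the timetable were applied to it.

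**5. Size.**
- Patients covered by the section 13 window, read literally: 0 of 200.
- Treatment blocks without a toxicity item: 3 of 4.
- Patients with no treatment-specific toxicity table for any of their treatment: 200 × *s*, where *s* is the share never given systemic therapy. The documents do not give *s*. If it is assumed to lie between 10% and 50%, the count is 200 × 0.10 = 20 to 200 × 0.50 = 100. These patients would rely on the generic row. The figures are not a count of missed events.

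**The case against.** The strongest reply has four parts.

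*Section 13 is a pharmacovigilance rule.* It sets reporting deadlines for live follow-up under cemiplimab and was probably never meant for anonymous chart abstraction. That is a fair reading, but the section does not limit itself to the prospective cohort, and no other AE-specific window replaces it.

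*The CRF has a place for any event.* The generic AE row is not restricted to systemic therapy, section 11.2 applies it to both cohorts, and section 7.3 allows causality to be assigned to procedures. This stands. A reader might infer that the objective cannot be met for surgery or radiotherapy, or that retrospective events will be undercounted. The documents do not support either statement, because such events can be entered. What the row lacks is a date and a treatment link.

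*The timetable is evidently the prospective schedule.* It has a consent row and counts months from start of treatment. This also largely stands, and it makes the baseline mismatch a smaller matter. The two tables still disagree, and baseline is the only entry comparable to a single documentation point.

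*No comparison of AE rates between cohorts is planned.* Section 8.1 excludes hypothesis testing, and section 14.3.2.2 keeps secondary outcomes descriptive. That is correct. But section 5.2 motivates the study by outcomes before and after approval, so readers will set the cohorts side by side. A reader might go on to infer a specific multiple from 36 months of prospective follow-up against a shorter retrospective course. The documents give neither a retrospective collection period nor an AE rate, so no such ratio can be derived.

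**Conclusion.** The point holds as a gap in definition and an unevenness in recording. The protocol promises retrospective safety by treatment option, including surgery and radiotherapy. It fixes no AE window for that cohort and gives only systemic therapy a dated, treatment-linked toxicity table. It also contradicts itself on baseline AE recording. All 200 retrospective patients are affected by the missing window, and three of the four treatment blocks by the missing item.

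Under-recording of non-systemic toxicity is a plausible risk whose size is unknown. This rests on two assumptions: that sites abstract what the CRF lists and little more, and that the e-CRF follows the section 9 tables. The matter is worth correcting in the protocol because it concerns what sites collect. It does not touch the primary endpoint.

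**What to change.** 1. State in section 13 that the consent-based window applies to the prospective cohort only. Set a retrospective AE abstraction window tied to diagnosis or treatment dates and consistent with the periods in sections 7.1 and 9.
2. Reuse the existing toxicity table in the surgery, locoregional and radiotherapy blocks. Alternatively, add an event date and a treatment link to the generic AE row.
3. Reconcile the baseline AE entry between the CRF table and the e-CRF timetable in section 9.
4. State in the report that AE frequencies in the two cohorts come from different ascertainment and are not directly comparable.

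Limiting retrospective events to serious, high-grade or discontinuation-related ones, or ending collection at the next treatment, would be optional choices and is not needed for this correction.

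The cost is a short paragraph, reuse of a table that already exists and somewhat longer abstraction per chart. The real limit is timing: the data are anonymous and documented once, so the added fields may not be recoverable for charts already entered. The report should say how many charts that concerns.
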